Analysis Plan: We will measure coronary plaque volume using CCTA images at both baseline and 12-months post-treatment initiation. The primary endpoint will be (1) total coronary plaque volume (continuous). Secondary endpoint will be non-calcified coronary plaque volume (continuous). Other outcome measures include (1) calcified plaque volume (continuous), (2) low-attenuation plaque volume (continuous), (3) coronary artery calcification score (continuous), and (4) coronary vessel stenosis (ordinal). The change in endpoint metrics between baseline and 12-month will be estimated for leuprolide versus relugolix versus no ADT. Data transformation to fit statistical assumptions will be done as needed. In addition, we will implement multivariable models that control for potential confounders (e.g. age, statin medication use) using general linear regression and/or logistic regression.

Power: We hypothesized that there will be significantly greater total plaque burden (i.e. summation of total plaque volume of all major coronary territories) increase from baseline to month 12 following GNRHa versus no ADT or relugolix. Using a standard deviation of 30 mm³ for the change in total plaque volume from scans obtained at two time points approximately 12 months apart in the study, 60 participants (30 in each comparative treatment arm) with both baseline and month 12 CCTA would provide 80% power to detect a difference of ≥ 20 mm³ in the change in total plaque volume [$P(X>Y) 0.72$] from baseline to 12 months.

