Analysis Plan: Immune responses (e.g., frequency or function of immune populations) and circulating proteomic biomarkers will first be summarized and plotted by the follow-up time points to illustrate the change pattern over time for all patients and then separated by treatment arms. We will first test whether these biomarker change pattern would be altered by treatment groups (e.g., GNRH-agonist versus GNRH-antagonist) using Kruskal-Wallis test, and then we will link such pattern (e.g., percentage change from baseline for biomarkers) with related CV injury metrics as in Aim 1 using the similar statistical strategy as in Aim 1.2. P-value will be adjusted for multiple testing using Holm-Bonferroni method to control familywise error rate.

Aim 3: To determine how pre-existing genomic alterations promoting inflammatory immunity impact development of CV toxicity following GNRHa versus relugolix, pre-treatment PBMC samples will be subjected to whole exome sequencing to determine alterations to the protein-coding regions of the genome. DNA will be extracted from PBMC and analyzed for quality. Following this analysis, DNA will be fragmented using restriction enzymes and undergo a second round of quality control. Fragmented DNA will be used to generate next-generation sequencing libraries and will undergo capture for exomic DNA sequences (Illumina Nextera Rapid Capture Expanded Exome), followed by amplification and repeated QA/QC. DNA sequencing will be conducted using the Illumina HiSeq platform. The FASTQ data files will be aligned using BWA-MEM, and variants from the human genome will be determined using VarScan and annotated using ANNOVAR. To be considered a valid mutation it will need to comprise at least 2% of the reads, as has been utilized to identify CHIP-related mutations^{27,55}.

Protocol Title: Mechanism and Predictors of Cardiotoxicity after Prostate Cancer Treatment: A Parallel Cohort and Randomized Trial Comparing Radiation Alone, Radiation plus Leuprolide, and Radiation plus Relugolix

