Subaim 1.1. Relationship between ADT and accelerated coronary plaque development/rupture									
Subaim 1.2. How baseline cardiac imaging biomarkers correlate with ADT-associated plaque development									
Aim 2. Relationship between leuprolide versus relugolix on immune effector responses implicated in atherosclerosis									
Subaim 2.1. How pre-existing and ADT-augmented inflammatory immune responses impact CV toxicity									
Subaim 2.2. How circulating proteomic biomarkers predict for cardiac toxicity									
Aim 3. How pre-existing genomic alterations impact development of cardiac toxicity following leuprolide versus relugolix									
Subaim 3.1: Identification of how pre-existing genomic alterations impact immune responses and CV toxicity									

10. Inclusion and Exclusion Criteria

Inclusion:

- Men ≥18 years old
- Non-metastatic prostate cancer
- Non-metastatic, biochemically recurrent prostate cancer
- Plan to undergo curative-intent pelvic radiation therapy (photons or protons) with or without brachytherapy

Exclusion:

- Metastatic prostate cancer requiring >24 months of ADT
- Prior invasive cancer diagnosis
- Prior exposure to androgen deprivation therapy
- Prior exposure to chemotherapy, immunotherapy, or radiation therapy

Protocol Title: Mechanism and Predictors of Cardiotoxicity after Prostate Cancer Treatment: A Parallel Cohort and Randomized Trial Comparing Radiation Alone, Radiation plus Leuprolide, and Radiation plus Relugolix

- History of cardiac bypass surgery, percutaneous coronary intervention, or cardiac device implantation
- Renal insufficiency, contrast allergy, or arrhythmias that limits feasibility of CT acquisition

11. Vulnerable Populations

Not applicable. This study does not involve individuals who are vulnerable to coercion or undue influence, such as pregnant women, children/minors, cognitively-impaired, prisoners, etc.

12. Local Number of Participants

Our accrual goal for this protocol is 90 patients (n=30 in each arm).

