Based on current prostate cancer volume at Winship Cancer Institute, accrual is expected to be complete in 12 months. Specifically, approximately 40 new patients with localized intact or recurrent PCa eligible for XRT (with or without ADT) are seen at all Winship sites monthly. We predict an enrollment rate of 20% with a low dropout rate, given that the final blood draw and coronary CT will occur 12 months after treatment initiation, which corresponds to the time of first or second standard post-treatment follow up appointment after completion of therapy.

Clinical research coordinators will screen all prostate cancer radiation oncology providers (directed by PI [name]) for all eligible patients to enroll. Co-investigators will be responsible for consenting patients in radiation oncology clinic.

13. Recruitment Methods

Patients will be recruited from those seen at the Department of Radiation Oncology at Winship Cancer Institute (EUH, EUHM, ESJH, EPTC). A brief description of the study will be given verbally to the patients, followed by written informed consent, and any relevant supplemental material as needed. The patients will be given ample time to review the consent and a time for questions and answer will be provided.

Study Enrollment Procedures

A copy of the institution's IRB-approved informed consent document and written justification for any changes made to the informed consent for this protocol must be on file at the Online Collaborative Research Environment (OnCore, <https://oncore.emory.edu>) and available to the Emory University Office for Clinical Research) before any patients may enter. The Winship Cancer Center institution consent form must be reviewed and approved and all documents must be received (i.e., IRB approved documentation, IRB approved consent form, etc.).

Patient Registration

All patients entering this study will be registered with the Clinical Trials Office (CTO) at the Winship Cancer Institute, Atlanta, GA. The CTO is open Monday through Friday from 8am-5pm (EST). OnCore will be used to record information for all registered patients including their assigned patient ID.

Study personnel will notify Winship Central Subject Registration (WCSR) by email at [contact], once subject has been consented for a trial.

Email notification must be done within 24 hours after consent has been obtained and it will include scanned copies of:

- Signed patient consent form
- HIPAA authorization form

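### The power statement for the primary endpoint gives no alpha, sidedness or test; at two-sided 5% its inputs give about 72% power, not 80%, and under normality P(X>Y) is 0.68, not 0.72

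*Combined protocol and SAP*

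**What the plan says.** The only power statement for the primary endpoint is the Power paragraph under Aim 1 in section 6. Its SD assumption is worded "Using a standard deviation of 30 mm³ for the change in total plaque volume". With 30 men in each compared arm, all having a baseline and a month-12 scan, it claims that the study "would provide 80% power to detect a difference of ≥ 20 mm³ in the change in total plaque volume". A bracketed P(X>Y) of 0.72 is attached to that difference.

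The Aim 1 Analysis Plan names no primary test. It says "The change in endpoint metrics between baseline and 12-month will be estimated for leuprolide versus relugolix versus no ADT", allows data transformation where needed, and adds multivariable models "using general linear regression and/or logistic regression". A rank test of treatment groups appears only in the Aim 2 Analysis Plan, which asks whether biomarker patterns "would be altered by treatment groups (e.g., GNRH-agonist versus GNRH-antagonist) using Kruskal-Wallis test". The Holm-Bonferroni adjustment is also confined to Aim 2 and carries no alpha level.

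Section 12 sets enrolment: "Our accrual goal for this protocol is 90 patients (n=30 in each arm". On losses it says only "We predict an enrollment rate of 20% with a low dropout rate".

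**The concern.** Power cannot be checked without an alpha, a sidedness and a test, and here all three are missing for the primary endpoint. When the usual two-sided 5% comparison of means is filled in, the stated SD, difference and arm size fall short of 80%.

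The P(X>Y) figure raises a separate problem. It describes the size of the effect, so it does not depend on alpha or sidedness. It should agree with 20 mm³ over 30 mm³, and under normality it does not.

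At stake is what the randomised GNRHa versus relugolix comparison can detect. Section 2 hypothesises that the GNRHa effect will be absent with relugolix, so detecting a difference between these arms is central to the trial's argument. An overstated power figure would make a failure to find one look more informative than the design supports.

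**Working it through.** **Inputs** (section 6, Aim 1, Power): difference 20 mm³; SD of the change 30 mm³; n = 30 per arm; claimed power 80%; claimed P(X>Y) 0.72. Standardised difference d = 20/30 = 0.667.

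**1. Can the 80% be reproduced?** For a two-sample t-test the noncentrality is d × √(n/2) = 0.667 × √15 = 2.582, with 58 degrees of freedom. The critical values are 2.002 (two-sided 5%) and 1.672 (one-sided 5%).

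| Method, 30 per arm, d = 0.667, normal data | Two-sided 5% | One-sided 5% |
|---|---|---|
| t-test (noncentral t) | 71.9% | 81.8% |
| Normal approximation, Φ(2.582 − z) | 73.3% | 82.6% |
| Wilcoxon, simulated | about 70% | about 80% |
| Wilcoxon, Noether's formula | 68.2% | 78.5% |

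On normal data, about 80% is recovered at one-sided 5% (equivalently two-sided 10%) and not at two-sided 5%.

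**2. What would give 80% at two-sided 5% by t-test?** Any one of these:
- 37 per arm (36 gives 79.7%, 37 gives 80.8%);
- at 30 per arm, d = 0.736, that is 0.736 × 30 = 22.1 mm³ (P(X>Y) about 0.70);
- at 30 per arm and 20 mm³, an SD of 20/0.736 = 27.2 mm³.

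**3. Does 0.72 agree with 20/30?** For normal data with equal SDs, P(X>Y) = Φ(d/√2) = Φ(0.667/1.414) = 0.681. In reverse, 0.72 requires d = √2 × Φ⁻¹(0.72) = 0.824. That is 0.824 × 30 = 24.7 mm³ at SD 30, or an SD of 20/0.824 = 24.3 mm³ at 20 mm³.

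**4. Does 0.72, taken as the effect, give 80%?** At two-sided 5% with 30 per arm, d = 0.824 gives 88.1% by t-test. Noether's formula, Φ(√(3N) × |P − 0.5| − z) with N = 60, gives Φ(13.416 × 0.22 − 1.960) = Φ(0.992) = 83.9%. At one-sided 5% the t-test gives 93.4%.

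**5. Does non-normality change this?** The next table simulates a shift of 20 with SD 30 and 30 per arm, tested at two-sided 5%. None of these distributions is stated in the plan.

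| Distribution of the change | P(X>Y) | Wilcoxon | t-test |
|---|---|---|---|
| Normal | 0.68 | 70% | 72% |
| t, 10 df | 0.69 | 73% | 72% |
| t, 5 df | 0.70 | 79–80% | 73% |
| t, 4 df | 0.71 | 83–84% | 74% |
| Laplace | 0.71 | 83% | 72–73% |
| Gamma, shape 4 | 0.70 | 77% | 72–73% |
| Gamma, shape 2 | 0.71 | 83–84% | 72–73% |
| Exponential | 0.74 | 92% | 73% |

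A comparison of means stays at 72–74% throughout. Only a rank test gains power as the tails or the skew grow.

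**6. Illustrations from assumptions not in the plan.**
- A 10% loss, to 27 per arm, gives 67% two-sided or 78% one-sided by t-test.
- Splitting alpha equally over the two named comparisons (GNRHa versus relugolix, GNRHa versus no ADT) gives 61% two-sided.
- Adjusting for covariates correlated 0.40 to 0.45 with the change would raise two-sided power to 79–81%.

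**The case against.** The strongest reply is that the 80% has not been shown to be wrong. The hypothesis is directional, and a one-sided 5% test gives 81.8% by t-test and about 80% by Wilcoxon. P(X>Y) is also the natural effect measure for a Wilcoxon calculation. Under Noether's formula at two-sided 5%, 0.72 needs 27.03 per arm for 80% power, so 30 per arm meets the target with some margin. Normality is nowhere assumed, and the plan foresees transformation.

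One set of assumptions even reconciles every figure. A Wilcoxon test at two-sided 2.5% on skewed data (gamma, shape 1.5), with shift 20 and SD 30, gives P(X>Y) of 0.724 and about 80% power. Covariate adjustment could also recover the shortfall. Finally, a finished trial is judged on its estimate and interval, which the power wording does not alter.

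Much of this stands as a limit on the claim: 72% is the power under a stated convention, and the 80% may have come from a calculation the plan does not describe. It does not remove the defect. A directional hypothesis does not declare a one-sided test, and one-sided testing rescues the 80% but not the 0.72 under normality. The reading that fits everything needs a rank test, a split alpha and a particular skewed distribution, none of them stated. The only analysis named for Aim 1 is regression, and an unadjusted regression of the change has the power of the t-test. No covariate correlation is given to support a gain from adjustment.

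**Conclusion.** The concern holds. As written, the 80% cannot be verified. Under an unadjusted two-sided 5% comparison of means it is overstated by about 8 points (71.9%), so the risk of missing a true 20 mm³ difference is about 28% instead of 20%. About 80% is reached at one-sided 5%, or at two-sided 5% with a rank test on clearly non-normal data.

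Under normality with equal SDs, 20/30 and P(X>Y) of 0.72 are inconsistent whatever alpha is used. They can be brought together only by a distributional assumption that the plan does not make.

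Separately, the evaluable number behind the power equals planned accrual, so any loss lowers power. The size of that effect depends on a dropout rate that the plan does not give. The trial is not invalidated, but the paragraph should be corrected.

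**What to change.** Keep the sample size. State the test, alpha, sidedness and assumed distribution behind the 80%, name the primary test for GNRHa versus relugolix in the Aim 1 Analysis Plan, and make the figures agree. Which wording applies depends on what was calculated:

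- **Two-sided 5% comparison of means.** Suggested text: *With 30 evaluable men per arm and an SD of 30 mm³, a two-sided 5% t-test has about 72% power for a 20 mm³ difference in 12-month change (P(X>Y) = 0.68 under normality) and 80% power for about 22 mm³.*
- **One-sided 5% test.** Say so, and correct P(X>Y) to 0.68 under normality.
- **Rank-based calculation on non-normal data.** State the distribution and any split of alpha, reconcile 0.72 with 20/30, and name that rank test for the primary comparison.

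In each case, also give the power at a plausible number of completers, with the assumed loss stated.

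The cost is a reworded paragraph and one named test, with no extra patients. Under the first option the stated power becomes less favourable.

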The role of inflammatory immune responses in potentiating CV disease ties directly in with the increased risk of CV disease following ADT in that ADT has long been shown to modulate systemic and prostate-infiltrating inflammatory immune responses. These include the induction of thymic regrowth and release of naïve T cells into circulation, an increase in various inflammatory immune populations (both myeloid and lymphocytes, particularly CD4+ Th1 cells), and decreased numbers of regulatory T cells³⁰⁻³⁵. While these enhanced responses following GNRH_a treatment has been well-established, the immunomodulatory effects of the GNRH-antagonist relugolix remain to be explored, as do the relationship between these enhanced inflammatory responses and increased CV disease.

Understanding biological mechanisms of ADT-associated CV toxicity, especially the difference between that of GNRH_a and GNRH-antagonists, will enhance our ability to decide on appropriate treatment strategies for PCa men receiving ADT, depending on an individual's risk for CV injury. Additionally, we will explore novel associations between patient-level clinical and genomic features and baseline imaging biomarkers with ADT-associated CV toxicity. By identifying major contributors to CV risk from ADT, we ultimately plan to develop a precision medicine approach to optimize risk prediction and allow clinicians to appropriately counsel patients on risk-benefit ratio of ADT and utilize novel risk-reducing ADT agents such as relugolix.

4. Study Endpoints

Aim 1: To identify and compare the association of GNRH-agonist leuprolide versus GNRH-antagonist relugolix with accelerated coronary plaque development in men with prostate cancer

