Aim 2.1: To determine how pre-existing and ADT-augmented inflammatory immune responses impact CV toxicity, we will evaluate pre-treatment, 3-, 6-, and 12-month peripheral blood mononuclear cells (PBMC) samples from all patients enrolled on trial. We will first evaluate the frequency and function of inflammatory immune populations by flow cytometry. While we will include a comprehensive panel evaluating lymphocyte and myeloid populations, we will specifically conduct an in-depth analysis quantifying the frequency, phenotype, and activation of T cells and macrophages. In particular, we will evaluate the frequency of naïve (CD44-CD62L+), effector memory (CD62L^{lo}CCR7-CD27^{lo/int}), central memory (CD62L^{hi} CCR7^{hi} CD44^{hi}), CD4 T-helper subsets (staining for the transcription factors Tbet, EOMES, ROR γ , and GATA), and CD4+ Tregs cells (CD25+GITR+CD127-Foxp3+)⁴⁷. Circulating macrophages will be evaluated for inflammatory M1 (CD80, CD86) and immunosuppressive M2 (CD163, CD206) sub-populations. Immune cells will also be evaluated for expression of GNRH receptors, as well as function by expression of intracellular cytokines associated with T cell activity (including IFNy, TNF α , IL-2, IL-4, IL-6, IL-10, and Granzyme B as we have published^{48,49}) or macrophage activity (Arg1, TNF σ , IL-6, IL-12).

Protocol Title: Mechanism and Predictors of Cardiotoxicity after Prostate Cancer Treatment: A Parallel Cohort and Randomized Trial Comparing Radiation Alone, Radiation plus Leuprolide, and Radiation plus Relugolix

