Aim 2.2: To determine how proteomic biomarkers associated with inflammatory immunity correspond with CV toxicity following ADT, we will conduct in-depth proteomic profiling, which has previously been utilized and validated to identify signatures associated with inflammatory immune responses and cardiovascular risk^{50,51}. To evaluate whether these signatures are associated with CV toxicity following ADT using leuprolide but not relugolix, pre-treatment and 12-month post-ADT PBMC will be subjected to proteomic profiling in conjunction with the Emory Integrated Proteomic Core as published by our colleagues at the Winship Cancer Institute⁵². Using nanocapillary liquid chromatography coupled with tandem mass spectrometry, this technology will be used to analyze patient PBMC samples for highly sensitive protein identification, posttranslational site mapping, and protein quantification. Briefly, PBMCs will be thawed under controlled conditions, sonicated in the presence of lysis buffer, protease inhibitors and phosphatase inhibitors. Protein samples will be sequentially digested, desalting, and dried under vacuum. Following reconstitution, samples will be loaded and eluted from a silica column driven by a UPLC system, monitoring elution spectra on a Fusion Mass Spectrometer. The mass spectrometry scans will be collected at a resolution of 120,000 at m/ 200 in profile mode while in a higher-energy collision dissociation fragmentation MS/MS spectra. Following sequencing, the combined *Homo sapiens* UniProt subsets will be used as references for proteomics searches. Data will be normalized to account for systematic differences in protein signal distributions, by aligning the medians of the log₂ protein signal distributions. Pathway enrichment will be conducted using gene sets obtained from the KEGG Pathway and MSigDB databases.

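### Aim 2.2 profiles unsorted PBMC without using the planned flow fractions, so it cannot tell a change in cell mix from a change in protein per cell (minor)

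*Combined protocol and SAP*

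**What the plan says.** The proteomic work is Aim 2.2 in Section 6 (it appears as Subaim 2.1 in Section 4).

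- **Material.** "pre-treatment and 12-month post-ADT PBMC will be subjected to proteomic profiling". In preparation, "PBMCs will be thawed under controlled conditions, sonicated in the presence of lysis buffer, protease inhibitors and phosphatase inhibitors". No sorting or enrichment of a cell type is described.
- **Normalisation.** "Data will be normalized to account for systematic differences in protein signal distributions", done "by aligning the medians of the log₂ protein signal distributions". KEGG and MSigDB pathway enrichment comes next.
- **Expected biology.** Section 3 (Background) says ADT leads to "an increase in various inflammatory immune populations (both myeloid and lymphocytes, particularly CD4+ Th1 cells), and decreased numbers of regulatory T cells". It gives no sizes and treats the immune effects of relugolix as still unknown.
- **Cell composition.** Aim 2.1 measures it on PBMC at baseline, 3, 6 and 12 months, which covers both proteomic draws: "We will first evaluate the frequency and function of inflammatory immune populations by flow cytometry".
- **Analysis.** Under the Analysis Plan that follows Aim 2.2, "circulating proteomic biomarkers will first be summarized and plotted by the follow-up time points". Groups are then compared by Kruskal-Wallis and the changes are linked to the CV metrics, with Holm-Bonferroni adjustment.

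No part of the plan brings the flow fractions into the proteomic analysis.

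**The concern.** In a bulk lysate, the signal of a protein concentrated in one lineage depends on two things: how much each cell of that lineage makes, and what share of the PBMC that lineage forms. If treatment moves the share, the protein moves even when no cell has changed its expression. All proteins of that lineage move together, which is the pattern that an enrichment analysis looks for.

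Section 4 presents Aim 2 as giving mechanistic insight into inflammatory immunity. More inflammatory cells is one mechanism and more inflammatory protein per cell is another. Aim 2.1 already measures the first. As written, Aim 2.2 could restate the Aim 2.1 cell counts under a pathway name, and a reader could not tell.

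**Working it through.** The plan gives no power, SD or effect size for the proteomics, so there is no figure of its own to reproduce. The check has a textual part and a numerical illustration.

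**1. Is composition handled anywhere in Section 6?**
- Aim 2 Analysis Plan: Kruskal-Wallis takes no covariates.
- The link to CV metrics follows an Aim 1.2 strategy, but Section 6 contains no Aim 1.2 analysis plan to consult.
- Aim 1 Analysis Plan: age and statin use are the example covariates. Cell fractions are not named.
- Aim 3 Analysis Plan: Spearman correlations between marker types, at baseline only. These cannot separate the components of a 12-month change.

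**2. Can median alignment remove the effect?** It subtracts one constant per sample from all log2 values. A change confined to one lineage's proteins survives unless most proteins move with it.

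**3. Size of the artefact.** Let f be the lineage's share and r its expression relative to other cells. With no per-cell change,

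log2 change = log2{[f1·r + (1 − f1)] / [f0·r + (1 − f0)]}.

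For a protein found only in that lineage this becomes log2(f1/f0), which is the upper bound. All fractions, and r = 10, are assumptions.

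| Share of PBMC | Lineage-only protein | 10-fold enriched, before normalisation | 10-fold enriched, simulated after median alignment |
|---|---|---|---|
| 20% to 22% | 0.14 | log2(2.98/2.80) = 0.09 | 0.07–0.08 |
| 20% to 25% | 0.32 | log2(3.25/2.80) = 0.21 | 0.20–0.22 |
| 20% to 30% | 0.58 | log2(3.70/2.80) = 0.40 | 0.38–0.39 |
| 20% to 40% | 1.00 | log2(4.60/2.80) = 0.72 | 0.67–0.69 |

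Median alignment removes almost none of it.

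**4. Would single proteins be declared significant?** Simulation assumptions, none from the documents: 2000 proteins, 200 enriched in the shifting lineage and 200 in the other cells; 3 groups of 30; between-man SD of the fraction and SD of its change both 3 points; shift in the GNRHa arm only; Kruskal-Wallis with Holm at 0.05; 20 replicates. Share of lineage-enriched proteins flagged:

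| Share of PBMC | Residual SD 0.3 | 0.5 | 0.8 |
|---|---|---|---|
| 20% to 22% | 0% | 0% | 0% |
| 20% to 25% | 1.4% | 0.4% | 0.02% |
| 20% to 30% | 59% | 4.4% | 0.3% |
| 20% to 40% | 100% | 79% | 11% |

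With the change in fraction added to a linear model, at most 0.02% were flagged in any setting. This is a best case, because the fraction was entered without measurement error.

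**5. Would a pathway be declared enriched?** Similar assumptions, with a 50-protein set wholly of the shifting lineage, a rank-sum test at 0.05/300 and 200 replicates. At residual SD 0.3, 0.5 and 0.8:
- 20% to 22%: flagged in 87, 63 and 33% of runs (a repeat with another random seed gave 94, 58 and 27%).
- 20% to 25%: 100% throughout (repeat 98.5 to 100%).
- No mean shift: 9, 7 and 0% (repeat 20, 6 and 0.5%). Even a chance imbalance in cell mix can trigger the set, because this test ignores correlation between proteins.
- After adjustment for the change in fraction: 0% in every shifted setting.

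The plan names no enrichment test, and a set drawn purely from one lineage is the extreme case. The result shows that Holm on single proteins does not protect a pathway statement.

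**The case against.** **The arm comparison may look confounded.** It is not. Between randomised arms, cell mix is measured after randomisation and may itself be an effect of treatment. More inflammatory cells is one form of the hypothesised effect. The bulk difference is a valid total effect, and whether a signature is associated with CV toxicity is a biomarker question that needs no per-cell attribution. This objection stands, and it limits the point to interpretation.

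**A reader might infer that a cell-mix shift will be reported as inflammation.** The documents do not support that. They give no shift size and no SD, and small shifts rarely passed Holm for single proteins. Section 3 covers systemic and prostate-infiltrating responses together, reports rises in both myeloid cells and lymphocytes, gives no PBMC proportions, and leaves relugolix open. A shift that differs between the two ADT arms is a hypothesis.

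**Other readouts exist.** Aim 2.1 also measures intracellular cytokines and activation, and plasma goes to a multiplex assay with ELISA validation. Inflammatory conclusions therefore do not rest on the lysate alone. That lowers the stakes but does not help interpret a given protein or pathway result.

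**The laboratory description is a summary.** Other processing steps may exist. Any step that applies one correction to a whole sample would leave a lineage-specific shift in place.

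**Calling the markers circulating.** A reader might take this as an error, since plasma is not what Aim 2.2 assays. PBMC are circulating cells and the protocol uses the word that way elsewhere, so the term is defensible.

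**Conclusion.** The point holds as a limit on interpretation. Aim 2.2 assays unsorted PBMC, median alignment is its only stated normalisation, and the flow fractions from the same draws go unused. Its protein and pathway results are therefore composition plus expression, and on their own cannot support a claim of activation per cell.

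The size is not known from the documents. Under the assumptions shown, a shift from 20% to 30% moves 10-fold enriched proteins by about 0.4 log2, and the share declared significant runs from 0.3% to 59% with the assumed SD. Pathway tests are more easily triggered, subject to the caveats given.

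The randomised contrast and any association with CV metrics stand as total or predictive statements. The primary CCTA endpoint is unaffected. Severity is minor.

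**What to change.** Keep the planned unadjusted analysis and add to Aim 2.2:

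1. A pre-specified sensitivity analysis that refits each protein's log2 change in a linear model with treatment group and the same-draw change in the major flow-measured fractions. Use a few lineage fractions and the key T-cell subsets the Aim 2.1 panel yields, such as Th1 and regulatory T cells. Broad lineages alone would miss the within-T-cell shifts that Section 3 names. Fix the list in advance. Aim 2.1 promises a lymphocyte and myeloid panel but does not list every lineage fraction, so confirm what it yields.
2. Pathway enrichment on both versions, reported side by side.
3. A reading rule. Unadjusted results are composition plus expression. A result is described as altered expression or activation beyond cell mix only if it persists after adjustment. The adjusted model does not veto the unadjusted arm difference or the association with CV metrics.

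**Cost.** Plan wording and analysis code; no new samples. The adjusted model conditions on a possible mediator, so it can remove real effects that act through cell mix. With six fractions (an assumed number), residual degrees of freedom in the two randomised arms fall from 60 − 2 = 58 to 52. Collinearity with arm matters more. For one fraction shifting by d with within-arm SD of change s, the variance of the arm effect is multiplied by 1 + d²/(4s²) if residual variance is unchanged. With s = 3 points (assumed), d = 2, 5 and 10 points give 1.11, 1.69 and 3.78, so the standard error grows by factors of 1.05, 1.30 and 1.94. A result that does not persist after adjustment should therefore be called unresolved rather than attributed to cell mix.
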